7.5.2 Adverse Events

Adverse events will be summarized by treatment group and pooled B244 treatment using the Medical Dictionary for Regulatory Activities (MedDRA) system organ class and preferred term. Separate tabulations will be produced for all treatment-emergent AEs (TEAEs), treatment-related TEAEs (those considered by the Investigator as at least possibly drug related), treatment-emergent SAEs (TESAEs), discontinuation from study due to TEAEs, deaths due to TEAEs, TEAEs by severity, and TEAEs occurring in $\geq 2\%$ of any study arm. By-subject listings will be provided for all treatment-emergent AEs.

STATISTICAL ANALYSIS PLAN

Version 3.0 12-Jan-22

Any treatment emergent AEs related to local safety (e.g., erythema, edema, induration, vesiculation, etc.) will be collected by the investigator during scheduled clinic visits. In addition, solicited patient assessment of local tolerability at application site (e.g., new itching, new rash, new pain/tenderness, new burning/stinging, new skin redness/color change, etc.) and grade will be collected during the first week of treatment using eDiary to inform local skin tolerability. Investigator will determine if any new local tolerability symptom or exacerbation of an existing symptom due to treatment warrants recording as an AE.

A summary of the incidence of any adverse event, SAE, and adverse events leading to discontinuation will be presented. Summaries will display, by treatment group and pooled B244 treatment, the incidence of patients with events, the frequency of patients with events within each primary system organ class and by preferred terms. For each preferred term and each system organ class a patient will be counted only once. For summaries on severe or drug-related AE, for a given patient, the highest severity or relationship for a specific preferred term will be considered.

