7.3 Study Withdrawal and Withdrawal from Investigational Product and Stopping Criteria

A participant may withdraw from the study at any time at his/her own request, or may be withdrawn at any time at the discretion of the Investigator.

Reasons for withdrawal (participants who refuse to complete any remaining study visits) or discontinuation (participants who prematurely stop the application) at any time during the study may include, but are not limited, to the following:

- For safety reasons, either at the discretion of the Investigator or at the participant's request
- For protocol violations at the discretion of AOBiome
- Withdrawal of consent by the Subject
- Lost to follow-up
- Due to use of concomitant therapy that could interfere with the results of the study (the Investigator will report all such information through the CRF and decide, in accordance with AOBiome, whether the participant is to be withdrawn).

The reason for participant study withdrawal will be recorded in the electronic Case Report Form (eCRF). Data from participants withdrawing from the study will be considered evaluable up to the point at which they are withdrawn using the same criteria for evaluability as for participants who complete the study.

Study stopping rules will be implemented to stop the study for safety review in the event that:

- 1 subject reports death, or
- >2 subjects report an SAE, or
- >4 subjects experience grade 3 AEs of a similar type, or
- >6 subjects experience grade 2 AEs of a similar type

when the reported SAEs or AEs are considered possibly, probably, definitely or related to the investigational product.

Atopic Dermatitis is an active disease with known seasonal and personal histories of flares and exacerbations of the patient's underlying disease state. This includes personal histories of worsening itch and itch-scratch cycles, which can lead to localized infection and localized cellulitis. A subject's known and collected clinical history should be considered by the principal investigator when determining relationship of event to the investigational product.

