8.9 Study Drug Discontinuation

Subjects will be discontinued from study drug treatment in the following events:

- The subject experiences a Grade 2 or higher treatment emergent AE that is assessed as likely related to study drug
- The subject receives treatment with an excluded therapy or has a clinically significant change in dose or frequency of allowed adjunctive therapies during the treatment period
- The female subject becomes pregnant or female partner of a male subject becomes pregnant or is breastfeeding

Discontinuation from study drug treatment may also occur for any of the following reasons:

- Subject decision to discontinue study drug treatment, or subject decision to withdraw consent from the study
- Any medical condition that may jeopardize the subject's safety if study drug is continued, in the investigator's and/or Sponsor's opinion
- Discontinuation is deemed to be in the best interest of the subject, in the investigator's and/or Sponsor's opinion

Subjects who discontinue treatment with study drug prior to completing the treatment period will have an ETD visit within 7 days after their last dose of study drug in addition to a follow-up visit

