12.4.2 Adverse Events

All adverse events (AEs) recorded during the study through the date of randomization through 28 days after the last dose of study drug will be analyzed.

Adverse events will be summarized by treatment group using the Medical Dictionary for Regulatory Activities (MedDRA) system organ class and preferred term. Separate tabulations will be produced for all treatment-emergent AEs (TEAEs), treatment-related AEs (those considered by the Investigator as at least possibly drug related), SAEs, discontinuations due to AEs, and AEs \geq Grade 3 severity. By-subject listings will be provided for any deaths, SAEs, and AEs leading to discontinuation.

AE's will be summarized using incidence rates. Therefore, each subject will only contribute once for a given adverse event SOC or PT.

Any treatment emergent AEs related to local safety (e.g., erythema, edema, induration, vesiculation, etc.) will be collected by the investigator during scheduled clinic visits. In addition, solicited local adverse reactions (e.g., itching, new rash, pain, tenderness, stinging, skin color change, etc.) and severity from subjects will be collected during the first week of treatment using eDiary to inform local skin tolerability.

A summary of the incidence of any adverse event, SAE, and adverse events leading to discontinuation will be presented. Summaries will display, by treatment group, the incidence of patients with events, the frequency of patients with events within each primary system organ class and by preferred terms. For each preferred term and each system organ class a patient will

be counted only once. For summaries on severe or drug-related AE, for a given patient, the highest severity or relationship for a specific preferred term will be considered.

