12.4.4 Adverse Events leading to treatment discontinuation

Adverse events leading to treatment discontinuation will be summarized overall and by primary system organ class and preferred term.

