| | Previous Day for Patient Reported | | |
| | Local Tolerability | | |
| 14.3.6.2 | Shift from Previous Day for Patient | Safety | Unique |
| | Reported Local Tolerability | | |
| 14.3.7 | Summary of Values and Change from | Safety | Repeat |
| | Baseline for Vital Signs | | - |
| 14.3.8.1 | Summary of Prior Medications by ATC | Safety | Unique |
| | Class Level 1 and Preferred Term | | - |
| 14.3.8.2 | Summary of Concomitant Medications | Safety | Repeat |
| | by ATC Class Level 1 and Preferred | | - |
| | Term | | |
| 14.3.8.3 | Summary of Rescue Medications by | Safety | Unique |
| | Class | | |

| 14.3.9.1 | Summary of Values and Change from | Safety | Unique |
|----------|-------------------------------------|--------|--------|
| | Baseline for Rescue Medication Days | | |
| | for All Subjects | | |
| 14.3.9.2 | Summary of Values and Change from | Safety | Unique |
| | Baseline for Rescue Medication Days | | |
| | for Subjects Who Took At Least One | | |
| | Rescue Medication | | |
| 14.3.10 | Summary of Medical History by | Safety | Unique |
| | System Organ Class and Preferred | | |
| | Term | | |

Table 14.3.1 Overall Summary of Treatment Emergent Adverse Events (Safety Population)

| | | B244 O.D. 5.0 | B244 O.D. 20.0 | Pooled B244 | Vehicle |
|--|-----------|---------------|----------------|-------------|-----------|
| | Statistic | (N=xx) | (N=xx) | (N=xx) | (N=xx) |
| Total Number of TEAEs [1] | n | XX | XX | XX | XX |
| Total Number of TESAEs | n | XX | XX | XX | XX |
| Number of Subjects with: | | | | | |
| At Least One TEAE [2] | n (%) | xx (xx.x) | xx (xx.x) | xx (xx.x) | xx (xx.x) |
| At Least One Treatment-Related TEAE [3] | n (%) | xx (xx.x) | xx (xx.x) | xx (xx.x) | xx (xx.x) |
| At Least One Severe (Grade 3) TEAE | n (%) | xx (xx.x) | xx (xx.x) | xx (xx.x) | xx (xx.x) |
| At Least One Treatment-Related Severe (Grade 3) TEAE | n (%) | xx (xx.x) | xx (xx.x) | xx (xx.x) | xx (xx.x) |
| At Least One TEAE Leading to Study Discontinuation | n (%) | xx (xx.x) | xx (xx.x) | xx (xx.x) | xx (xx.x) |
| At Least One TEAE Leading to Death | n (%) | xx (xx.x) | xx (xx.x) | xx (xx.x) | xx (xx.x) |
| At Least One TESAE [4] | n (%) | xx (xx.x) | xx (xx.x) | xx (xx.x) | xx (xx.x) |
| At Least One Treatment-Related TESAE [3] | n (%) | xx (xx.x) | xx (xx.x) | xx (xx.x) | xx (xx.x) |

[1] TEAE: Treatment-Emergent Adverse Event – defined as any AE with onset after the first dose of study medication through 28 days after the last dose of study medication.

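### The SAP reports adverse events leading to study discontinuation only, although protocol 12.4.4 commits to a summary of those leading to treatment discontinuation

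*SAP*

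**What the plan says.** Protocol 12.4.4 has its own heading for this output and states it without condition: "Adverse events leading to treatment discontinuation will be summarized overall and by primary system organ class and preferred term". Protocol 12.4.2 lists "discontinuations due to AEs" among the planned tabulations without saying what is discontinued.

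The SAP is more specific, in a different direction. The list of separate tabulations in SAP 7.5.2 contains "discontinuation from study due to TEAEs". The overall TEAE table (14.3.1) has the row "At Least One TEAE Leading to Study Discontinuation". Table 14.3.1.5 gives the breakdown by class and term for discontinuation from the study. The adverse event detail listing (16.2.7.2) and the COVID-19 event listing (16.2.7.3) each carry a single flag, for study discontinuation. The disposition table (14.1.1.1) gives reasons for leaving the study only. The last paragraph of SAP 7.5.2 says that a summary of "adverse events leading to discontinuation will be presented", again without saying discontinuation of what. The safety endpoint in SAP 3.2.4 is equally unqualified.

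**The concern.** Stopping the drug and leaving the study are different events in this trial. A table of adverse events that made subjects stop the product is a standard tolerability output, and the protocol commits to it. If the SAP counts only exits from the study, a subject whose drug was stopped for an adverse event, but who stayed under observation, is not identified as a discontinuation for an adverse event. The protocol's stated summary would then not be delivered, and a reader of the report would not be told so.

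**Working it through.** No arithmetic applies. The plan states no figure on this point, so the check is to compare the texts and follow one subject through the outputs.

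**1. Are the two events distinct?** Yes. Protocol 7.3, repeated in SAP 4.2, separates withdrawal, meaning refusal of the remaining visits, from stopping application early. Protocol 8.9 lists events after which study drug is stopped, among them: "The subject experiences a Grade 2 or higher treatment emergent AE that is assessed as likely related to study drug". It then says that subjects who stop drug before the end of the treatment period "will have an ETD visit within 7 days after their last dose of study drug in addition to a follow-up visit". Stopping drug therefore does not by itself end participation.

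**2. Is there a SAP output for drug stops?** No. The safety tables in SAP Appendix A and the listings in Appendix B contain none for adverse events leading to discontinuation of study drug. Table 14.3.5 summarizes product weights and diary counts. Listing 16.2.5.3 gives dose dates but does not link them to an adverse event.

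**3. Is the change declared?** No. SAP 7.7 lists changes from the protocol's planned analyses, and this is not among them.

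**4. One subject followed through.** Take a subject who stops drug in Week 2 because of a TEAE, attends the visit after the last dose, and returns at Week 8.

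| Output | Result for this subject |
|---|---|
| General TEAE tables (class and term, severity, relationship) | Event appears |
| Table 14.1.1.1 | Can count as a completer, since its footnote asks only for completion through Week 8 |
| Table 14.3.1, discontinuation row | Not counted if recorded as remaining in the study |
| Table 14.3.1.5 | Not counted, same condition |
| Listing 16.2.7.2, discontinuation flag | No, same condition |
| Summary committed to in protocol 12.4.4 | Should be counted; no such output exists |

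**5. Size.** Let D be the number of subjects who stop drug for an adverse event and c the share of them recorded as remaining in the study. The undercount is D × c, which lies between 0 and D. The documents give neither D nor c.

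**The case against.** Three points can be made for the SAP.

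**The SAP wording is not uniform.** SAP 3.2.4 and the closing paragraph of 7.5.2 do not limit discontinuation to the study, and in the protocol 12.4.2 is also unqualified. It is fair to say that the restriction sits in one phrase of 7.5.2 and in the shells. It does not rescue the plan, because every shell that implements the unqualified text says study discontinuation.

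**Drug stops may be recorded as study exits.** A reader might infer that every drug stop for an adverse event in a subject who attends Week 8 is missed. The documents do not support that. The synopsis gives the Early Termination Visit, timed within 7 days of the last dose, to participants who have left the study early, and protocol 10.6.8 ties that visit to withdrawal before Day 56. Protocol 11.6 asks a completer to have made all study visits. Sites could therefore record some or all drug stops as study discontinuations. This objection stands as a limit on size.

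**The efficacy imputation is not shown to be affected.** A reader might infer that subjects who stop drug for an adverse event but stay in the study escape non-responder imputation. SAP 7.4 already applies that rule to subjects who stop treatment early, and its TEAE condition does not mention the study. The inference requires programmers to use the listing's study-discontinuation flag, which no section says. What remains is an unstated term.

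It is also true that the adverse event stays in the general tables and that local tolerability is tabulated separately. What is lost is the classification, not the event.

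**Conclusion.** The mismatch is real and should be corrected. Protocol 12.4.4 commits to one output, the SAP specifies a different one, and SAP 7.7 does not disclose the change. Followed as written, the SAP can leave a drug stop for an adverse event unclassified when the subject remains in follow-up.

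The size is unknown. It depends on how many subjects stop drug for an adverse event and on how sites record them. It could be zero, and any figure for the undercount would rest on an assumed rate. No effect on the primary analysis or on the NRI results is established.

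**What to change.** Beside the existing study-discontinuation outputs, add three items for TEAEs leading to discontinuation of study drug: a row in Table 14.3.1, a table by system organ class and preferred term, and a column in Listing 16.2.7.2. Amend SAP 7.5.2 to name both kinds of discontinuation.

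Derive the flag from the adverse event record if it captures the action taken with study drug. The CRF is not among the documents, so this cannot be confirmed. Otherwise, derive it from the last-dose date, which SAP 7.5.1 shows is held in the EDC, together with the discontinuation reason. If the output will not be produced, record the departure from protocol 12.4.4 in SAP 7.7.

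As a clarification only, state in SAP 7.4 that the TEAE condition in the NRI rule means discontinuation of study drug, which agrees with the rule's reference to stopping treatment early. In the addendum, state which kind applies to the WOCF rule.

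The cost is one table, one row, one listing column and a few sentences. It rises if no action-taken field exists and the flag has to be rebuilt from dosing dates and reasons.

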7.5.3 Prior and Concomitant Medications

Prior and concomitant medications will be coded using the World Health Organization (WHO) dictionary version Mar 2020 or later. Prior medication is defined as any medication with a stop date prior to the date of first dose of study drug. Concomitant medication is defined as any medication with a start date on or before the date of last dose of study drug and a stop date on or after the date of first dose of study drug.

Prior and concomitant medications will be summarized by Anatomic Therapeutic Class (ATC) Level 1 and Preferred Term by treatment group and pooled B244 treatment. Patients taking the same medication multiple times will be counted once per medication. Previous and concomitant medications will also be presented in a data listing.

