5 STUDY DESIGN

- This is a Prospective, Vehicle Controlled, Double-Blind, Multicenter, Randomized Phase II Trial, comparing the effect of twice daily B244 applications for 4 weeks vs vehicle applications on treatment of mild to moderate pruritus associated with atopic dermatitis.
- Approximately 576 subjects may be enrolled.
- The total duration of the study will be approximately 11 weeks. Participants will report for a Screening visit and if all inclusion/exclusion criteria are met, subjects will go through a two-week washout phase (see Section 10.6.2) before reporting for a Baseline visit.
- After screening and baseline, participants will be randomized to one of two doses of B244 or vehicle application for 4 weeks.
- Randomization will be 1:1:1 so that an equal number of patients will be treated in each Arm of the study.
- All B244 randomized subjects will be treated at the dose of $1x10^{10}$ cells/ml (O.D. 5.0) or $4x10^{10}$ cells/ml (O.D. 20.0).
- Subjects must be willing and able to complete diary within a consistent time frame on a daily basis and to comply with restrictions on allowable therapies for the duration of the study.
- All subjects will attend a screening visit not more than 21 days prior to Baseline (Day 0). Subjects will be required to return to the clinic at Baseline, Day 14 (Week 2) and Day 28 (Week 4) visits. All subjects will be asked to attend a Week 8 follow-up visit 4 weeks (28 (±3) days) after the last dose of study medication.
- Subjects will apply a total of 10 pumps of IP per application across all affected areas twice-a-day (i.e. 10 pumps in the morning and 10 pumps again at night) for 4 weeks.
- Safety evaluations will consist of review of participant's medical history at screening and on-going assessment of adverse events reported throughout the study duration.

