8.13 Concomitant and Excluded Therapies

Any medication or vaccine (including over-the-counter or prescription medicines, vitamins, and/or herbal supplements) that the subject is receiving within 30 days prior to screening and through the final study visit will be recorded on the appropriate CRF) along with:

- Reason for use.
- Dates of administration including start and end dates.
- Dosage information including dose and frequency.

Any medications started during the study (including "as needed" medications) will be recorded in the concomitant medication list as soon as the Investigational Site will become aware of the medication being added.

Details of any medication taken by the subject outside of the study center will be reviewed by the Investigator or designee on each study center visit. The Medical Monitor should be contacted if there are any questions regarding concomitant or prior therapy.

A list of excluded medications/therapy is provided in Appendix B.

Previous treatment of atopic dermatitis must be recorded irrespective of the term it was given. Acetaminophen is permitted for use any time during the study. Other concomitant medication may be considered on a case-by-case basis by the Investigator in consultation with the Medical Monitor.

Concomitant therapies include any therapies (including over-the-counter medications) used by a subject from initiation of study drug treatment through the follow-up period. A record of all medications used will be maintained for each subject throughout the study. Reported information will include a description of the type of drug, treatment period, dosing regimen, the route of administration, and drug indication.

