8.13.1 Permitted Medications

Subjects using oral contraceptives, hormone-replacement therapy, or other maintenance therapies that are not Excluded Therapies (Appendix B) may continue their use during the study.

Stable doses of the following therapies for pruritus and/or atopic dermatitis will be allowed as adjunctive therapies during the study:

- Oral H1 antihistamines
- Bland emollients

A detailed guideline will be shared with the sites and subjects to ensure consistency in study medication treatment application and relation to body washing, emollient use, and other chemical exposure to skin.

Low- or mid-potency topical corticosteroids will be allowed per subjects' usual medication, frequency, and dose throughout the study from screening to washout, treatment, and follow-up periods as rescue medication up to 7 days per month.

Subjects using any of these adjunctive therapies should maintain their regimen without clinically significant changes in type, dose or frequency throughout the screening, treatment, and follow-up periods.

All participants will be screened for concomitant medications prior to inclusion into the study. Any concomitant medication to treat adverse events will be recorded in the Concomitant Medication section of the eCRF.

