6.5.8 Safety Parameters

Safety and tolerability endpoints will consist of all adverse events (AEs) reported during the study duration from the date of randomization through Week 8 (End of Study Visit). Specific AEs are defined below.

STATISTICAL ANALYSIS PLAN

Version 3.0 12-Jan-22

Treatment-Emergent Adverse Events (TEAE): Any AE with onset after the first dose of study medication through 28 days after the last dose of study medication.

Serious Adverse Event (SAE): An AE occurring at any dose that results in any of the following outcomes: death, a life-threatening AE, in-patient hospitalization or prolongation of existing hospitalization, a persistent or significant disability/incapacity, or a congenital anomaly/birth defect.

Associated with Use of the Study Drug: There is a reasonable possibility that the experience may have been caused by the study drug. If the Investigator does not know whether or not study drug caused the event, then the event will be handled as "related to study drug" for reporting purposes. The determination of whether an AE is related to study drug is as follows:

- Related: The AE has a missing, unknown, possible, probable or definite relationship to the study medication.
- Not related: The AE is unlikely or definitely unrelated to the study drug.

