| ATC Class Level 1 #1 [2,3] | n (%) | xx (xx.x) | xx (xx.x) | xx (xx.x) | xx (xx.x) |
| Preferred Term #1 | n (%) | xx (xx.x) | xx (xx.x) | xx (xx.x) | xx (xx.x) |
| Preferred Term #2 | n (%) | xx (xx.x) | xx (xx.x) | xx (xx.x) | xx (xx.x) |
| Preferred Term #3 | n (%) | xx (xx.x) | xx (xx.x) | xx (xx.x) | xx (xx.x) |
| etc. | | | | | |
| ATC Class Level 1 #2 | n (%) | xx (xx.x) | xx (xx.x) | xx (xx.x) | xx (xx.x) |
| Preferred Term #1 | n (%) | xx (xx.x) | xx (xx.x) | xx (xx.x) | xx (xx.x) |
| Preferred Term #2 | n (%) | xx (xx.x) | xx (xx.x) | xx (xx.x) | xx (xx.x) |
| Preferred Term #3 | n (%) | xx (xx.x) | xx (xx.x) | xx (xx.x) | xx (xx.x) |
| etc. | | | | | |

[1] Percentage and all subsequent percentages based on the number treated.
[2] Subjects will be counted once per ATC Class/Preferred Term.
[3] WHO Drug Dictionary version YYYYMMM was used to code medication names.

Source: Listing XXXX PROGRAM NAME: XXXXXXXXXX

DATE: HH:MM/DDMMMYYYY

Programming Note:

• Repeat for 14.3.8.2 Summary of Concomitant Medications by ATC Class Level 1 and Preferred Term for Safety Population

Table 14.3.8.3 Summary of Rescue Medications by Class (Safety Population)

| | Statistic | B244 O.D. 5.0 | B244 O.D. 20.0 | Pooled B244 | Vehicle |
|--|------------------|--|--------------------------------------|--|--|
| | Statistic | | (IN=XX) | (IN=XX) | (IN=XX) |
| Number of Subjects with at Least One Rescue Medication [1] | n (%) | xx (xx.x) | xx (xx.x) | xx (xx.x) | xx (xx.x) |
| Class 4: Mid-Strength [2] | | | | | |
| Clocortolone pivalate (0.1%) | n (%) | xx (xx.x) | xx (xx.x) | xx (xx.x) | xx (xx.x) |
| Mometasone furoate (0.1%) | n (%) | xx (xx.x) | xx (xx.x) | xx (xx.x) | xx (xx.x) |
| Triamcinolone acetonide (0.1%) | n (%) | xx (xx.x) | xx (xx.x) | xx (xx.x) | xx (xx.x) |
| Betamethasone valerate (0.1%) | n (%) | xx (xx.x) | xx (xx.x) | xx (xx.x) | xx (xx.x) |
| Fluocinolone acetonide (0.025%) | n (%) | xx (xx.x) | xx (xx.x) | xx (xx.x) | xx (xx.x) |
| Class 5: Lower Mid-Strength | | | | | |
| Fluticasone propionate (0.05%) | n(%) | vv (vv v) | vy (vy v) | vv (vv v) | vv (vv v) |
| Prednicarbate (0.1%) | n (%) | лл (лл.л) хх (хх х) | | $\mathbf{X} (\mathbf{X} \mathbf{X} \mathbf{X})$ | $\mathbf{x} \mathbf{x} (\mathbf{x} \mathbf{x} \mathbf{x})$ |

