Weeks 3 - 4 rescue medication days = number of rescue medication days from Day of Visit 3 to Day of Visit 4 - 1.

Weeks 1 - 4 total rescue medication days = number of rescue medication days from Day 1 to Day of Visit 4 - 1.

Weeks 5 - 6 rescue medication days = number of rescue medication days from Day of Visit 4 to Day of Visit 4 + 13.

Weeks 7 - 8 rescue medication days = number of rescue medication days from Day of Visit 4 + 14 to Day of Visit 5 - 1.

Weeks 5 - 8 total rescue medication days = number of rescue medication days from Day of Visit 4 to Day of Visit 5 - 1.

[2] Each time interval is normalized as a rate where (# Rescue Medication Days) = [(# Days Rescue Medications Used in Interval) / (# Actual Days in Interval)] * (# Expected Days in Interval).

[3] CFB = Change from Baseline.

Source: Listing XXXX PROGRAM NAME: XXXXXXXXX

| | | B244 O.D. 5.0 | B244 O.D. 20.0 | Pooled B244 | Vehicle |
|---------------------|----------------------|----------------------|----------------------|--|----------------------|
| Visit [1,2] | Statistic [4] | (N=xx) | (N=xx) | (N=xx) | (N=xx) |
| Baseline | n/N (%) | xx/xx (xx.x) | xx/xx (xx.x) | xx/xx (xx.x) | xx/xx (xx.x) |
| | Mean (SD) | xx.x (xx.xx) | xx.x (xx.xx) | xx.x (xx.xx) | xx.x (xx.xx) |
| | Median | XX.X | XX.X | XX.X | XX.X |
| | Min, Max | XX, XX | XX, XX | XX, XX | XX, XX |
| Washer 1 2 | m/NI(0/) | / () | | | |
| weeks $1-2$ | n/N(%) | XX/XX (XX.X) | XX/XX (XX.X) | XX/XX (XX.X) | XX/XX (XX.X) |
| | Median | XX.X (XX.XX) | XX.X (XX.XX) | XX.X (XX.XX) | XX.X (XX.XX) |
| | Median | XX.X | XX.X | XX.X | XX.X |
| | Min, Max | XX, XX | XX, XX | XX, XX | XX, XX |
| Weeks 1 – 2 CFB [3] | Ν | XX | XX | XX | XX |
| LJ | Mean (SD) | xx.x (xx.xx) | xx.x (xx.xx) | xx.x (xx.xx) | xx.x (xx.xx) |
| | Median | XX.X | XX.X | XX.X | XX.X |
| | Min, Max | XX, XX | XX, XX | XX, XX | XX, XX |
| | | | | | |
| Weeks $3 - 4$ | n/N (%) | xx/xx (xx.x) | xx/xx (xx.x) | xx/xx (xx.x) | xx/xx (xx.x) |
| | Mean (SD) | xx.x (xx.xx) | xx.x (xx.xx) | xx.x (xx.xx) | xx.x (xx.xx) |
| | Median | XX.X | XX.X | XX.X | XX.X |
| | Min, Max | XX, XX | XX, XX | XX, XX | XX, XX |
| Weeks 3 – 4 CFB | Ν | XX | XX | XX | XX |
| | Mean (SD) | xx.x (xx.xx) | xx.x (xx.xx) | xx.x (xx.xx) | XX.X (XX.XX) |
| | Median | XX.X | XX.X | XX.X | XX.X |
| | Min, Max | XX, XX | XX, XX | XX, XX | XX, XX |
| Wests 1 4 Tetel | $\sim D I (0/)$ | | | | |
| weeks 1 – 4 Total | n/N (%) Maar (SD) | XX/XX (XX.X) | XX/XX (XX.X) | XX/XX (XX.X) | XX/XX (XX.X) |

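### Non-rescue medications first started after the last dose fall in neither the prior nor the concomitant table, contrary to Protocol 8.13 and not declared in SAP 7.7

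*SAP*

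**What the plan says.** SAP 7.5.3 gives two definitions. For the earlier category: "Prior medication is defined as any medication with a stop date prior to the date of first dose of study drug". For the later one: "Concomitant medication is defined as any medication with a start date on or before the date of last dose of study drug", with the further condition that the stop date is not before the first dose. Prior medications go to Table 14.3.8.1 and concomitant medications to Table 14.3.8.2, both by ATC Level 1 and preferred term, with each subject counted once per medication.

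Protocol 8.13 is wider: "Concomitant therapies include any therapies (including over-the-counter medications) used by a subject from initiation of study drug treatment through the follow-up period". Protocol 8.13.1 adds: "Any concomitant medication to treat adverse events will be recorded in the Concomitant Medication section of the eCRF". Appendix A of the protocol collects concomitant medication at Day 56 and at the Early Termination visit, so the records will exist.

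The SAP's treatment-emergent window (6.5.8) is: "Any AE with onset after the first dose of study medication through 28 days after the last dose of study medication". The protocol (Section 5) places the final visit accordingly, as a "Week 8 follow-up visit 4 weeks (28 (±3) days) after the last dose of study medication".

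SAP 7.7, which lists changes from the protocol's planned analyses, does not mention the concomitant-medication definition.

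**The concern.** The two SAP definitions leave a gap. A medication whose first use comes after the last dose did not stop before the first dose, so it is not prior, and it did not start by the last dose, so it is not concomitant. Under the protocol it is plainly concomitant.

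Two consequences follow. First, the safety tables fall out of step: an adverse event in the four weeks after the last dose is tabulated as treatment-emergent, but a non-rescue drug first started to treat it is not tabulated. Second, the cut-off is each subject's own last dose, so whether a given treatment is counted depends on whether the subject was still on study drug. Protocol 8.9 requires study drug to be stopped for certain related adverse events and then schedules further visits, so treatment begun just after stopping is a foreseeable case.

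**Working it through.** The plan gives no figure here to reproduce. The check applies both sets of rules to possible medication dates.

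**Inputs**
- SAP study-day numbering, first dose = Day 1 (SAP 6.5.2).
- Prior: stop < first dose. Concomitant (SAP): start ≤ last dose and stop ≥ first dose (SAP 7.5.3).
- Concomitant (protocol): any use from first dose through follow-up (Protocol 8.13).
- Follow-up visit 28 days after last dose (Protocol 5).

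**Step 1: individual cases, completer with last dose on Day 28 and follow-up to Day 56**

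| Medication dates | SAP 7.5.3 | Concomitant under Protocol 8.13? |
|---|---|---|
| Day -10 to Day -3 | prior | no |
| Day -10, ongoing | concomitant | yes |
| Day 10 to Day 12 | concomitant | yes |
| Day 28 to Day 30 | concomitant | yes |
| Day 29 to Day 33 | neither | yes |
| Day 40 to Day 45 | neither | yes |

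A medication begun by the last dose stays in the table however long it continues. Only first starts after the last dose drop out.

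**Step 2: size of the gap by possible start date**

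Unclassified share = (follow-up day − last-dose day) / follow-up day.

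- Completer, last dose Day 28: (56 − 28)/56 = 28/56 = 50%.
- Completer who also doses on the Visit 4 day, last dose Day 29: (57 − 29)/57 = 28/57 = 49%.
- Subject who stops on Day 10 (an illustrative assumption), follow-up 28 days later: (38 − 10)/38 = 28/38 = 74%.

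The ±3-day visit window moves the first figure between 25/53 = 47% and 31/59 = 53%, and the last between 25/35 = 71% and 31/41 = 76%. Under the protocol window the unclassified share is zero in every case.

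These are shares of the calendar in which a new start would go unclassified. They are not shares of medications or of subjects.

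**Step 3: dependence on stopping**

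Take two subjects with the same reaction on Day 10 and the same non-rescue treatment started on Day 11. If one had the last dose on Day 10, start 11 > last dose 10, so the treatment is not counted. If the other continues to Day 28, 11 ≤ 28, so it is counted.

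**Step 4: do the rescue tables fill the gap?**

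Only for allowed rescue steroids. Tables 14.3.9.1 and 14.3.9.2 cover follow-up; for Weeks 5–8 they define "total rescue medication days = number of rescue medication days from Day of Visit 4 to Day of Visit 5 - 1". Table 14.3.8.3 lists rescue products with no stated cut-off at last dose. But SAP 7.5.4 keeps other concomitant and prohibited medications out of the rescue-day counts, and the footnote to Table 14.3.8.3 restricts entries reported as other to the allowed list. A systemic antibiotic or a new antihistamine first started in follow-up is therefore in none of these tables.

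**Step 5: date imputation**

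SAP 6.5.7 sets a completely missing start date to the consent date, and partial dates to 1 January or the first of the month. Some undated or part-dated follow-up starts would therefore pass the start-date test and be counted, while fully dated ones would not.

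**The case against.** The strongest reply is that this is one descriptive table. Medication use is not a safety endpoint in either document, and treatment-emergent events, serious events and discontinuations due to events are tabulated in their own right, so the adverse-event signal is intact. Protocol 8.13 sits among the conduct and recording rules, and the synopsis promises summaries of concomitant medications without stating a window, so an on-treatment definition is a legitimate choice. All of that stands, and it is why a declared on-treatment window with a supplementary table would be an adequate remedy. It does not remove the undeclared conflict between the two definitions or the absence of any category for later starts.

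A reader might also infer more than the documents support:

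- **That everything started in follow-up vanishes.** It does not: allowed rescue steroids are tabulated through Week 8.
- **That treatment for an event leading to discontinuation is lost as such.** It is lost only if first started after the last dose. If begun on or before that day, it is counted.
- **That excluded therapies used in follow-up are hidden.** Appendix B of the protocol makes such use a violation to be recorded, Protocol 12.7 requires non-permitted medications to be summarised as deviations, and SAP 7.3.2 tabulates major deviations and lists all of them. That is not a display by ATC class and preferred term, but it is a display.
- **That the records are missing from all output.** Listing 16.2.13.1 has a prior yes/no flag and no stated last-dose cut-off. A follow-up start may well be listed with the flag set to no; its title leaves this unclear.

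**Conclusion.** The point holds for non-rescue medications first started after the last dose. By the SAP's own rules they are neither prior nor concomitant, which contradicts Protocol 8.13 and is not declared in SAP 7.7, while the treatment-emergent window continues for 28 more days.

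The gap is 28 of 56 possible start days for a completer and 28 of 38 for a subject stopping on Day 10. This assumes follow-up exactly 28 days after the last dose and complete start dates; the Day 10 stop is illustrative. It would be tempting to read the 50% as half of all medication use going unreported, but the table counts subjects ever using a medication, and drugs carried over from treatment remain in it. It would also be tempting to conclude that the table under-reports treatment of adverse events on B244. That would need more discontinuations for adverse events on B244 followed by newly started treatment, and neither document gives a figure for this. The number of medications affected and any imbalance between arms are unknown.

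No efficacy result or safety endpoint is affected. The correction is worth making because the rule as written gives a safety table that disagrees with the protocol and depends on when each subject stopped study drug.

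**What to change.** Either of two changes would do.

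1. In SAP 7.5.3, define concomitant medication as any medication used from the first dose through the last study visit, matching Protocol 8.13. In Table 14.3.8.2, show medications started on or before the last dose and those started after it as two subsets, and carry the same flag in Listing 16.2.13.1.
2. Keep the on-treatment definition, add a separate table for medications first started after the last dose, and record the departure from Protocol 8.13 in SAP 7.7.

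The first is preferable because it leaves one definition across both documents. The data are already collected, so the cost is a sentence in the SAP and one derived flag in the medication dataset. The downside is a longer descriptive table (or one additional table under the second option).
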